4.1.3. Deviations which Require Exclusion from the Per-Protocol Population

In accordance with SOP-130050 and the ARI114265 PDMP, deviations which require exclusion from the Per-Protocol population should be identified; the 19 deviations are listed in the below table. The historical term used to describe these deviations in ARI114265 protocol is 'major'. In this RAP and for future reporting the phrase 'deviations which require exclusion from the Per-Protocol population' will replace 'major'.

Number	Deviations which Require Exclusion from the Per-Protocol Population
01	Missed placebo run-in phase
02	Incorrect study drug (wrong treatment) consumed
03	Randomized but did not consume double-blind study drug
04	Cumulative study drug compliance <75%
05	Cumulative study drug compliance >125%
	Violation of Inclusion Criteria (protocol #)
06	Confirmed BPH clinical diagnosis (Inclusion 2)
07	IPSS ≥12 at Screening (Inclusion 3)
08	Prostate volume ≥30cc by TRUS at Screening (Inclusion 4)
09	PSA ≥1.5ng/ml and ≤10ng/mL at Screening (Inclusion 5)
10	Qmax >5 mL/sec and ≤15mL/sec with Voided Volume ≥125mL/sec at Screening (Inclusion 6)
	Violation of Exclusion Criteria (protocol #)
11	Any conditions other than BPH, which may in the judgement of the investigator, result in urinary symptoms or changes in flow rate (Exclusion 6)
12	Use of 5ARI within 6 months of Screening or historical TRUS and throughout the study (Exclusion 10a)
13	Use of anabolic steroids within 6 months of Screening and throughout the study (Exclusion

Number	Deviations which Require Exclusion from the Per-Protocol Population
	10b)
14	Use of phytotherapy for BPH within 2 weeks of Screening and throughout the study (Exclusion 10c)
15	Use of alpha-adrenoreceptor blockers within 2 weeks of Screening and throughout the study, except study meds (Exclusion 10d)
16	Use of alpha-adrenoreceptor agonists or anticholinergics or cholinergics within 48 hours prior to all uroflowmetry and IPSS assessments (Exclusion 10e)
17	Use of selective beta 3-adrenoreceptor agonist (mirabegron) within 2 weeks prior to all uroflowmetry and IPSS assessments (Exclusion 10f)
18	Prohibited medications and non-drug therapies of Protocol Section 6.2 and not otherwise classified above.
	Other
19	Any condition which should exclude a subject from the Per-Protocol population which is not included above; identified by Study Team.

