The number of post-randomization adverse events, the number and the percentage of subjects reporting any post-randomization AE will be summarized by treatment group for the following:

- All AEs
- Drug-related AEs
- Serious AEs
- AEs leading to study drug discontinuation
- AEs leading to withdrawal from study
- Fatal AEs

Comparisons of treatment groups for each of these sets of AEs will be performed using Fisher's Exact Test.

Total number of adverse events reported in the study as well as the number and percentage of subjects reporting at least one AE will be provided for each treatment group. Total number of AEs as well as the number and percentage of subjects reporting each AE will be reported by treatment group, primary system organ class and preferred term. On-treatment and post-treatment AEs will be summarized separately, as well as together as post-randomization AEs. Non-serious post-randomization AEs will be summarized by treatment group. A summary of post-randomization AEs will be provided by treatment group and six month time period of onset (Months 1-6, Months 7-12, Months 13-18, Months 19-24), by treatment group and age group (<65 years, \geq 65 years), by treatment group and age group (<75 years, \geq 75 years), and by treatment group and country.

A summary of post-randomization AEs will be provided by treatment group and preferred term by descending frequency of preferred term (regardless of system organ class). In addition, such summaries will be done for serious post-randomization AEs and also for non-serious post-randomization AEs.

For on-treatment AEs, the event rate per 100 person-years of study drug exposure will be summarized by treatment group, primary system organ class and preferred term overall and by time period (Months 1-6, Months 7-12, Months 13-18, Months 19-24).

A summary of post-randomization AEs will also be provided by treatment group and maximum intensity. If the same AE occurs on multiple occasions in the same subject, the AE with the highest intensity will be presented. Intensity will be categorized as mild, moderate, or severe; a category for missing/not applicable intensity will be included.

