11.8. Appendix 8: Adverse Event Time Periods and Special Adverse Event Definitions

Date-related derivations and transformations related to adverse events (AEs) are described below.

AE Onset Time since First Dose

= AE Onset Date – Treatment Start Date if treatment start date > AE onset date
= AE Onset Date – Treatment Start Date +1 if treatment start date <= AE start date
= missing otherwise

AE Duration (in days) = AE Resolution Date – AE Onset Date + 1

The timing of AEs will be categorized as follows:

- An AE is “Pre-Treatment” if the AE onset date is before the treatment start date.
- An AE is “On Treatment” if the AE onset date is on or after the treatment start date (but on or before the treatment stop date, if that is non-missing), or if the onset date is missing.
- An AE is “Post-Treatment” if the treatment stop date is non-missing, and the AE onset date is after the treatment stop date.
- An AE is “Post-Randomization” if the AE is either On Treatment or Post-Treatment.

Note: Cut-off dates are defined in [Appendix 6](#); definition is repeated here, in terms of 6-month treatment periods, since this is used to determine AE onset period:

Month k Cut-off Date (for k= 6, 12, 18, 24): The maximum of [Month k clinic visit date, Month k lab visit date, Baseline Date + (k * 91/3)].

An on-treatment AE is uniquely identified as having onset within one of the following four time periods: Months 1-6, Months 7-12, Months 13-18, or Months 19-24.

- An AE is considered to have onset in the Months 1-6 time period if it is an on-treatment AE and the onset date is on or before the Month 6 cut-off date.
- An AE is considered to have onset in the Months 7-12 time period if it is an on-treatment AE and the onset date is after the Month 6 cut-off date and is on or before the Month 12 cut-off date.
- An AE is considered to have onset in the Months 13-18 time period if it is an on-treatment AE and the onset date is after the Month 12 cut-off date and is on or before the Month 18 cut-off date.
- An AE is considered to have onset in the Months 19-24 time period if it is an on-treatment AE and the onset date is after the Month 18 cut-off date.

If the AE onset date is partially missing, the timing is determined as follows:

1. If the non-missing parts of the date (either just year or year/month) are unambiguously before the start of treatment, the AE is considered Pre-Treatment.

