11.15.5. Safety Tables

Safety	
3.1	Summary of Adverse Events Starting Post-Randomization by Type
3.2	Summary of Adverse Events Starting Post-Randomization
3.3	Summary of Adverse Events Starting On-Treatment
3.4	Summary of Adverse Events Starting Post-Treatment
3.5	Summary of Non-Serious Adverse Events Starting Post-Randomization
3.6	Summary of Adverse Events Starting Post-Randomization by Time Period of Onset
3.7	Summary of Adverse Events Starting Post-Randomization by Age Group (<65, ≥65)

Safety	
3.8	Summary of Adverse Events Starting Post-Randomization by Age Group (<75, ≥75)
3.9	Summary of Adverse Events Starting Post-Randomization by Country
3.10	Summary of Adverse Events Starting Post-Randomization by Descending Frequency
3.11	Summary of Serious Adverse Events Starting Post-Randomization by Descending Frequency
3.12	Summary of Non-Serious Adverse Events Starting Post-Randomization by Descending Frequency
3.13	Summary of Adverse Events Starting On-Treatment (Study Drug Exposure Basis)
3.14	Summary of Adverse Events Starting On-Treatment by Time Period (Study Drug Exposure Basis)
3.15	Summary of Adverse Events Starting Post-Randomization by Maximum Intensity
3.16	Summary of Most Common Adverse Events Starting Post-Randomization
3.17	Summary of Most Common Non-Serious Adverse Events Starting Post-Randomization
3.18	Summary of Drug-Related Adverse Events Starting Post-Randomization
3.19	Summary of Drug-Related Adverse Events Starting On-Treatment
3.20	Summary of Drug-Related Adverse Events Starting Post-Treatment
3.21	Summary of Drug-Related Adverse Events Starting Post-Randomization by Time Period of Onset
3.22	Summary of Drug-Related Adverse Events Starting Post-Randomization by Age Group (<65, ≥65)
3.23	Summary of Drug-Related Adverse Events Starting Post-Randomization by Age Group (<75, ≥75)
3.24	Summary of Drug-Related Adverse Events Starting Post-Randomization by Country
3.25	Summary of Serious Adverse Events Starting Post-Randomization
3.26	Summary of Serious Adverse Events Starting On-Treatment
3.27	Summary of Serious Adverse Events Starting Post-Treatment
3.28	Summary of Serious Adverse Events Starting Post-Randomization by Time Period of Onset
3.29	Summary of Serious Adverse Events Starting Post-Randomization by Age Group (<65, ≥65)
3.30	Summary of Serious Adverse Events Starting Post-Randomization by Age Group (<75, ≥75)
3.31	Summary of Serious Adverse Events Starting Post-Randomization by Country

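### The post-randomization adverse event tables by onset period have no period for an event that starts after the treatment stop date

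*SAP*

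**What the plan says.** Appendix 8 (SAP Section 11.8) sorts events by onset date. An on-treatment event starts "on or after the treatment start date (but on or before the treatment stop date, if that is non-missing"; an event with a wholly missing onset date is also on-treatment. An event is post-treatment "if the treatment stop date is non-missing, and the AE onset date is after the treatment stop date", and post-randomization "if the AE is either On Treatment or Post-Treatment".

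The onset periods follow: "An on-treatment AE is uniquely identified as having onset within one of the following four time periods". Each of the four definitions repeats the condition. Even the last period, which has no upper limit, applies only "if it is an on-treatment AE and the onset date is after the Month 18 cut-off date". The imputation of partial onset dates for period assignment is likewise written for on-treatment events.

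Section 8.2.2 asks for something wider: "A summary of post-randomization AEs will be provided by treatment group and six month time period of onset". It repeats the request for drug-related events, and Section 8.2.3 does so for serious events. Appendix 15 titles Table 3.6 "Summary of Adverse Events Starting Post-Randomization by Time Period of Onset"; Tables 3.21 (drug-related) and 3.28 (serious) have parallel titles. The notes to Table 5 make post-randomization the default unless a footnote says otherwise. Table 3.14 carries the on-treatment footnote; Tables 3.6, 3.21 and 3.28 carry none.

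**The concern.** The SAP separates the on-treatment by-period table (3.14) from the post-randomization by-period tables (3.6, 3.21, 3.28), then supplies a period rule only for the former. A programmer must either leave post-treatment events out of tables whose title includes them, or devise a rule that the SAP does not contain, possibly after unblinding.

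Such events are expected. Section 8.2.2 collects adverse events to the end of the two-year study period, and Tables 3.4, 3.20 and 3.27 exist to report those that start after treatment. At stake is whether a reader can trust the by-period tables to cover the population they name, and whether they agree with the overall tables.

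The same gap may reach the special-interest events. Section 8.2.4.2 puts these on a post-randomization basis, and Section 8.2.4.3 summarises time to first onset by time period of onset without saying which period rule applies.

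**Working it through.** The SAP states no figure on this point, so the check is of the rule itself.

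**1. The rule applied literally.** Take treatment start as day 0. Where no visit is later, the cut-off for month k is k × 91/3 days after baseline (Appendix 6): 182, 364, 546 and 728 days for k = 6, 12, 18 and 24.

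| Stop day | Onset on stop day | Onset 1, 30 or 120 days later |
|---|---|---|
| 150 | on-treatment, Months 1-6 (150 ≤ 182) | post-treatment, no period |
| 400 | on-treatment, Months 13-18 (364 < 400 ≤ 546) | post-treatment, no period |
| 728 | on-treatment, Months 19-24 (728 > 546) | post-treatment, no period |

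With the stop date missing, onsets on day 728 and 1, 30 or 120 days later are all on-treatment and fall in Months 19-24. An event with no onset date at all goes into the first period. So an undated event gets a period, while a fully dated one the day after a recorded stop does not.

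**2. Effect on reconciliation.** On-treatment and post-treatment events do not overlap and together make up the post-randomization events. In counts of events:

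- All events: Table 3.2 = Table 3.3 + Table 3.4. Under the literal rule the periods of Table 3.6 add up to Table 3.3 only, so the shortfall is Table 3.4.
- Drug-related: Table 3.18 = Table 3.19 + Table 3.20. Table 3.21 is short by Table 3.20.
- Serious: Table 3.25 = Table 3.26 + Table 3.27. Table 3.28 is short by Table 3.27.

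These shortfalls overlap, because drug-related and serious events are subsets of all events; they must not be added.

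**3. Illustrative size.** Assume that a fraction d of men stop at day 364 of 728 and remain under event collection to day 728, and that the event rate after stopping is h times a constant on-treatment rate. The share of post-randomization events without a period is

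d × 364 × h / [(1 − d) × 728 + d × 364 + d × 364 × h].

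- d = 0.10, h = 1: 36.4 / (655.2 + 36.4 + 36.4) = 5.0%.
- d = 0.20, h = 2: 145.6 / (582.4 + 72.8 + 145.6) = 18.2%.

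| Stop early | h = 0.5 | h = 1 | h = 2 |
|---|---|---|---|
| 5% | 1.3% | 2.5% | 4.9% |
| 10% | 2.6% | 5.0% | 9.5% |
| 20% | 5.3% | 10.0% | 18.2% |
| 30% | 8.1% | 15.0% | 26.1% |

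The share is 0 once the period rule covers post-treatment events.

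**The case against.** The best defence is that nothing disappears from the report. A post-treatment event is in the overall post-randomization table and in its own post-treatment table. The Fisher tests in Section 8.2.2 use overall post-randomization incidence, so none changes, and the by-period tables are descriptive. Table shells and the Program Safety Analysis Plan are separate documents; a shell may already carry a post-treatment column. Special-interest events are further protected: Section 8.2.4.3 also tabulates 6-month windows counted from treatment start with no on-treatment condition, and Appendix 8 censors their Kaplan-Meier estimates at the later of the last clinic visit and the latest event start, not at treatment stop. All this stands and limits the consequence. It does not remove the conflict between the definition and the tables within the SAP.

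A reader might go further and infer three things that the document does not support.

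- **That the exposure-adjusted rates lose events.** Tables 3.13 and 3.14 are declared on-treatment, and exposure ends on the same stop date as the event window. Leaving out events and person-time together does not by itself bias a rate. A lag added to both changes nothing if the rate after stopping equals the rate before; otherwise its direction depends on an unknown rate. A lag is a preference, not a correction.
- **That dutasteride is still acting after the stop date.** The SAP gives no half-life or duration of action. The per-protocol deviation "Use of 5ARI within 6 months of Screening or historical TRUS and throughout the study (Exclusion 10a") is an eligibility and prohibited-medication rule, and the same six months apply to anabolic steroids. The six-month questionnaire follows men whose sexual event has already led to withdrawal; it does not look for new onsets.
- **That the omission falls more on the combination arm.** This would need lasting drug action or unequal stopping, and the SAP gives figures for neither.

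**Conclusion.** The contradiction holds. As written, the period rule cannot place an event that starts after a recorded stop date, yet Tables 3.6, 3.21 and 3.28 are defined to include such events. Strictly, their placement is undefined: the SAP does not say that they are dropped, but that is what the literal rule produces. The special-interest line on time period of onset may inherit the gap.

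The consequence is confined to descriptive tables that do not match their titles or reconcile with the overall tables. The percentages above rest on assumed stopping, follow-up and event rates, and on complete collection after stopping; they show the possible scale and are not a forecast. No bias between arms and no fault in the exposure-adjusted rates is shown. The point should still be corrected, because the rule yields wrong contents for named safety tables and costs little to repair.

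**What to change.** In Appendix 8, for the post-randomization by-period displays (Tables 3.6, 3.21 and 3.28), define the four periods by onset date against the Month 6, 12 and 18 cut-off dates for every post-randomization event, dropping the on-treatment condition. Keep that condition for Table 3.14. State in Section 8.2.4.3 that the time-period-of-onset summary follows the post-randomization rule.

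Extend the partial-date imputation in the same way. This creates no conflict: a partially dated event is post-treatment only if its known month or year lies wholly after the stop date, so imputing the first day of that month or year still falls after it. The cut-off dates need no change, because the term counted from the baseline date exists even where a later visit was missed.

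Retitling the three tables, with the matching text and Table 5, as on-treatment, or adding a post-treatment column, would also remove the contradiction, but neither would show post-randomization events by period as Sections 8.2.2 and 8.2.3 promise.

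The cost is a few lines of SAP text and a small programming change, to be made before unblinding. No new data are needed.

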The time to first onset in days will be summarized by treatment group as a continuous variable as well as by time period of onset. In addition, time to first adverse event of special interest will be summarized by treatment group using estimates calculated by the Kaplan-Meier method and displayed graphically as Kaplan-Meier curves. Time to resolution for the first event in days will be summarized by treatment group.

Duration of adverse events of special interest will be summarized by treatment group for uncensored values, censored values, and all values. It is recognized that summary statistics such as means and medians involving censored values will be biased (low).

The number of sexual and breast adverse events leading to study withdrawal, as well as the number and percentage of subjects reporting at least one such sexual and breast adverse event will be provided for all event types and also by event type for each treatment group.

Resolution status at end of study (resolved, not resolved) and time from treatment stop date to AE resolution will be summarized by treatment group for the sexual and breast adverse events leading to study withdrawal and not resolved at Month 24 / End of Treatment visit.

Listings of sexual and breast adverse events of special interest will be provided. A listing of sexual and breast adverse event status data will be provided.

A listing of the TFUQ data for sexual and breast adverse events will be provided.

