2. If the non-missing parts of the date are unambiguously after the stop of treatment, the AE is considered Post-Treatment.
3. If #1 or #2 above cannot be assigned, then the AE is considered On-Treatment.

If an on-treatment AE onset date is partially missing, then, for the purpose of assigning the 6-month treatment period referenced above, the onset date will be imputed according to the algorithm described in the second paragraph below, and the imputed date will be used to assign the period.

An AE is considered drug-related if the relationship variable indicates so, or the variable value is missing. When an AE has an outcome of Resolved/Recovered with or without sequelae, it may be categorized for resolution status as follows: if resolution date is on or before treatment stop date, the AE is considered resolved on-therapy, or if either the resolution date or the treatment stop date is missing and the action taken is not 'investigational product withdrawn', the AE is considered resolved on-therapy. If a resolved AE is not resolved on-therapy, it is considered resolved off-therapy.

For the purpose of Kaplan-Meier estimates for Special Interest AEs, and for categorizing AEs by time intervals, the following algorithm will be used:

- 1) If an AE start date is partial, it will be imputed as follows:
 - a. If all components of the date (day, month and year) are missing, then the date will not be imputed, but the AE will be categorized in the first 6-month time period.
 - b. If both day and month are missing, then the day and month will be imputed as 01 January.
 - c. If only day is missing, then the day will be imputed as 01.
 - d. Any imputation described in items 1b and 1c above will be revised if it is in conflict with the treatment start date: if the month and year of treatment start date is same as those in the imputed date, the imputed date will be changed to the treatment start date.
- 2) A subject not having the particular AE will be censored at the latter of the following two dates: date of last clinic visit, latest AE start date.
- 3) If an AE end date is partial, it will be imputed as follows:
 - a. If all components of the date (day, month and year) are missing, then the end date will be missing.
 - b. If both day and month are missing, then the day and month will be imputed as 31 December.
 - c. If only day is missing, then the day will be imputed as the last day of the corresponding month.

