For computing AE duration, partial AE start and end dates will be imputed as previously described, and events with completely unknown (missing) end dates will be censored at the latter of the following two dates: date of last clinic visit, latest AE start date. AE duration is the total number of non-overlapping days for all events per subject, and will be considered censored if any contributing event is censored.

Time to death is defined as (date of death – treatment start date +1). For subjects who do not experience death, time to death is censored at the date of last clinic visit (if missing,

the subject will be censored at the treatment start date).

Special interest adverse events, including MedDRA preferred terms and codes, are presented below in [Table A](#)-[Table D](#):

Table A: Sexual and Breast Adverse Events of Special Interest

Table B: Prostate Cancer Adverse Events of Special Interest

Table C: Cardiovascular Adverse Events of Special Interest

Table D: Infrequent Tier 1 Adverse Events of Special Interest

Table A. Sexual and Breast Adverse Events of Special Interest: MedDRA Preferred Terms and Codes		
Special Interest Event	MedDRA Preferred Term	PT_Code
Altered (Decreased) Libido	Sexual dysfunction	10040477
	Male sexual dysfunction	10057672
	Libido decreased	10024419
	Loss of libido	10024870
	Libido disorder	10061221
Impotence	Erectile dysfunction	10061461
	Organic erectile dysfunction	10052004
	Disturbance in sexual arousal	10058929
	Psychogenic erectile dysfunction	10052005
Ejaculation Disorders	Ejaculation delayed	10014325
	Ejaculation disorder	10014326
	Ejaculation failure	10014328
	Retrograde ejaculation	10038967
	Anorgasmia	10002652
	Orgasm abnormal	10031085
	Premature ejaculation	10036596
	Male orgasmic disorder	10025513
	Orgasmic sensation decreased	10052449
	Semen volume decreased	10039944
Breast Disorders	Breast hyperplasia	10006256
	Breast enlargement	10006242
	Gynaecomastia	10018800
	Nipple disorder	10029417
	Breast engorgement	10006240
	Breast swelling	10006312
	Breast pain	10006298
	Breast tenderness	10006313
	Nipple pain	10029421
	Nipple swelling	10058680
Breast Disorders: Breast Enlargement	Breast discomfort	10049872
	Breast hyperplasia	10006256
	Breast enlargement	10006242
	Gynaecomastia	10018800
	Nipple disorder	10029417
	Breast engorgement	10006240
Breast Disorders: Breast Tenderness	Breast swelling	10006312
	Breast pain	10006298
	Breast tenderness	10006313
	Nipple pain	10029421
	Nipple swelling	10058680

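### Imputed adverse event end dates have no upper limit, and recovered events without an end date are right-censored, so special-interest event durations can be overstated

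*SAP*

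**What the plan says.** All of this is in SAP Appendix 8 (Section 11.8) unless another section is named.

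- **Partial end dates.** With only the year known (rule 3b): "If both day and month are missing, then the day and month will be imputed as 31 December". With month and year known (rule 3c): "If only day is missing, then the day will be imputed as the last day of the corresponding month". No limit follows.
- **Partial start dates.** These go to the first day of the known month, or to 1 January. A check is attached (rule 1d): "Any imputation described in items 1b and 1c above will be revised if it is in conflict with the treatment start date".
- **Completely missing end dates.** Rule 3a: "If all components of the date (day, month and year) are missing, then the end date will be missing". For duration, "events with completely unknown (missing) end dates will be censored at the latter of the following two dates", the two dates being the last clinic visit and the latest event start date. The recorded outcome plays no part.
- **Duration.** It is computed from the imputed dates and totalled over a subject's events without double-counting overlapping days. The total is censored if any contributing event is censored.
- **Resolved events without a date are expected.** One of the conditions that puts a resolved event in the on-therapy class begins: "if either the resolution date or the treatment stop date is missing and the action taken is not 'investigational product withdrawn', the AE is considered".

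Section 8.2.4.3 reports duration of special-interest events by treatment group for uncensored, censored and all values, and notes that summaries involving censored values are biased low. It also says: "Time to resolution for the first event in days will be summarized by treatment group". Sections 8.2.4.4 and 8.2.4.5 use the same format for prostate cancer and cardiovascular events.

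**The concern.** A recorded end date, even a partial one, means that someone learned of the recovery while the subject was still being followed. Recovery therefore cannot fall after death, last contact or data freeze. Rule 3 can put it there, and because only completely missing end dates are censored, the table then shows the result as a known duration.

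The second problem runs through the censoring. Right-censoring says that the event lasted at least until the censoring date. For an event already recorded as resolved, what is known is the reverse: it had ended by the time the resolution was recorded. The plan can thus call one event resolved on-therapy in one summary and treat it as still running in another. The reader is meanwhile told that any bias is downward.

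At stake is how long sexual, breast and other special-interest events appear to last in each arm.

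**Working it through.** The plan gives no figure on this point to reproduce, so I applied its rules to assumed dates. The formula, from Appendix 8, is duration = resolution date − onset date + 1.

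**1. Is there a limit elsewhere?** Rule 1d tests imputed start dates against treatment start. Rule 3 has no counterpart, and no other section supplies a cap or makes the censoring depend on outcome.

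**2. Partial end date.** Assume onset on 6 March 2016 and last contact (or death) on 15 March 2016.

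| End date recorded as | Imputed end | Days past last contact | Duration under plan | Duration if capped at last contact |
|---|---|---|---|---|
| 2016 | 31 Dec 2016 | 291 | 301 | 10 |
| March 2016 | 31 Mar 2016 | 16 | 26 | 10 |

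- From 15 March to 31 December: 16 + 30 + 31 + 30 + 31 + 31 + 30 + 31 + 30 + 31 = 291 days.
- Duration under the plan for the year-only date: onset to last contact is 9 days, so 9 + 291 + 1 = 301.
- Capped duration: 9 + 1 = 10.

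The overshoot past last contact in the same year is at most 364 days (365 in a leap year), or 30 days when only the day is missing. If last contact is assumed uniform over a 365-day year, the mean is the average of 365 − d for d = 1 to 365, which is 364 / 2 = 182 days. The month-end equivalent is 14.7 days.

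**3. Resolved event, no end date, later visits attended.** Assume onset on Day 90, recovery recorded at a visit on Day 183, and the last clinic visit on Day 729 with no later event start.

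- Plan: 729 − 90 + 1 = 640 days, censored.
- Bound from the visit that recorded recovery: 183 − 90 + 1 = 94 days at most.

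**4. Resolved event, no end date, against the plan's own label.** Assume onset on Day 90, treatment stop and last clinic visit on Day 200, drug not withdrawn for the event, and another event starting on Day 500.

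- Plan: 500 − 90 + 1 = 411 days, censored.
- Limit implied by classing the event as resolved on-therapy: 200 − 90 + 1 = 111 days.

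In cases 3 and 4 the censored value exceeds the longest duration possible, so the error for these events is upward.

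**The case against.** The best defence is that this is a narrow matter in descriptive tables. Earliest start with latest end is a simple prespecified rule, applied alike to both arms. Censored and uncensored values are shown separately, and no test or survival model of duration is planned. Late end dates can also be genuine: Section 8.2.2 has ongoing events monitored until resolution, stabilization or loss to follow-up, and some sexual-function events are followed for up to 6 months after the last dose. All of that stands. It means that durations can, rather than always do, run past what was possible, and that the last clinic visit would be the wrong cap. It does not justify a recovery date after death or last contact, or a resolved event counted as running.

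A reader might infer more than the plan supports:

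- **That the arm with more events is inflated more.** Duration is summarized among subjects with events, so the shift depends on the share of partial dates and the gaps involved, not their count. Nothing suggests that these differ by arm.
- **That recoveries shift from on- to off-therapy.** That classification has its own missing-date rule. Appendix 8 directs the imputation to Kaplan-Meier estimates, time intervals and duration only.
- **That time to resolution is affected.** The plan does not say that imputed end dates are used there.
- **That year-only start dates add a further 182 days.** That treats start and end as independent and ignores rule 1d. If both fall in one year as two ordered uniform dates, each is off by about 365 / 3 ≈ 122 days, or about 243 in total rather than 364.

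**Conclusion.** The point holds, with limited reach. Followed as written, rule 3b/3c can place a recovery after death, last contact or data freeze and report the duration as exact. The censoring rule can overstate duration for resolved events without an end date, which the caveat in Section 8.2.4.3 does not allow for.

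The individual errors can be large: 291 days past last contact in the first example, and a censored 640 days against a maximum of 94 in the second. These rest on assumed dates. The first mechanism needs a partial end date with death, last contact or data freeze before the imputed date. The second needs a resolved outcome with no end date. The plan does not give the number of such records, so the effect on the treatment-group summaries cannot be computed.

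Only the special-interest duration summaries are affected, plus time to resolution if imputed dates are used there. Efficacy endpoints, event incidence and Kaplan-Meier time to first event, which uses start dates, are untouched.

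**What to change.** In Appendix 8:

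1. In rule 3b and 3c, set the imputed end date to the earliest of the current rule's date, death, last contact and data freeze, and not before onset.
2. Restrict right-censoring of duration to events whose outcome is not resolved.
3. For resolved events with no end date, bound duration by the date on which recovery was recorded, if the database holds it. Otherwise report them as resolved with duration unknown. The SAP does not show such a variable, so its availability must be checked first.
4. State whether imputed end dates are used for time to resolution.

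In Section 8.2.4.3, amend the caveat so that it no longer implies that all bias is downward.

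The cost is a few sentences and a small change to the event derivation program. The cap uses dates that a trial database would normally hold. Only the recording date in item 3 may be unavailable, and the fallback there needs no new data. Counts of partial and missing end dates by arm would show how much the rules matter.
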